4.3 Selection and Withdrawal of Subjects

4.3.1 Inclusion Criteria

The study physician will make all medical eligibility and termination decisions. To be eligible, the subject must:

- 1. Be 14 to 20 years old, inclusive; we will exclude children < 14 due to diversity across adolescence and youths > 20 because our focus is teenagers
- 2. Self-report consuming alcohol ≥ 2 days/week on average in the past 28 days
- 3. Meet the DSM-5 criteria for AUD
- 4. Be interested in reducing alcohol use
- 5. Be able to verbalize an understanding of the consent/assent form, able to provide written informed consent/assent, verbalize willingness to complete study procedures, able to understand written and oral instructions in English and able to complete the questionnaires required by the protocol.
- 6. Have parent permission, if younger than 18 years
- 7. Be able to take oral medication and be willing to adhere to the medication regimen
- 8. Complete all assessments required at screening and baseline.
- 9. Agree to the schedule of visits, verbally acknowledge that s/he will be able to attend each scheduled visit, participate in phone visits and that s/he does not have any already scheduled events or a job that may substantially interfere with study participation.
- 10. Not anticipate any significant problems with transportation arrangements or available time to travel to the study site over the next 2 months.
- 11. Agree (if the subject is female and of childbearing potential) to use at least one reliable method of birth control, unless she is surgically sterile, partner is surgically sterile or she is postmenopausal. Examples of reliable methods include (but may not be limited to):
 - a. oral contraceptives
 - b. contraceptive sponge
 - c. contraceptive skin patch
 - d. diaphragm or condom
 - e. intrauterine contraceptive system
 - f. levonorgestrel implant
 - g. medroxyprogesterone acetate contraceptive injection
 - h. complete abstinence from sexual intercourse
 - i. hormonal vaginal contraceptive ring
 - i. surgically sterile
 - k. postmenopausal

1. partner is surgically sterile

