4.6 Measures Taken to Minimize/Avoid Bias

4.6.1 Randomization

If eligible for the study, subjects will be randomized in an approximate 1:1 ratio (N = 50; targeting 21 subjects per group – 42 subjects total) to either atomoxetine or placebo for 6 weeks. Urn randomization will ensure approximately equal representation of males and females.

If the subject is randomized and is never dispensed study drug, then the subject will be considered a randomization failure and an additional subject will be randomized with the next randomization sequence at the time s/he is randomized. Likewise, if the subject was randomized and then is determined to not be eligible for the study and never received study drug, then another subject will be randomized such that the total numbers of subjects who were eligible, randomized, and dispensed study drug meet the enrollment goals. In the case of a subject who was eligible, randomized, and dispensed study drug but did not return for follow-up visits, this subject will not be replaced. Any subject who received study drug but was later determined to be ineligible will likewise not be replaced. The reason(s) that a subject was considered a randomization failure or screen failure will be documented in source documents and case report forms (CRFs).

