Subjects desiring additional counseling or professional therapy for non-crisis psychiatric matters (e.g., family or relationship problems, transient school issues) will neither be discouraged from such activity nor asked to postpone until their study participation is concluded. Subjects who initiate outside psychotherapy during the study will not be withdrawn. Subjects may (or may not) be withdrawn if they start new medications, at the discretion of the study physician, if there are any safety concerns.

During the Study Week 5 clinic visit, subjects will complete a second H-LAB paradigm session, which will follow the same procedures as the pretreatment baseline assessment session.

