4.7 Human Laboratory Paradigm Testing (H-LAB)

During the Randomization/Baseline Visit (prior to taking the study medication) and in Study Week 5, subjects will be seen in-person in the clinic for the human laboratory paradigm testing. The human lab session will last for approximately 45 minutes. Laboratory sessions should occur in the late afternoon if possible. The subject must have BAC = 0.00 prior to starting the H-LAB session. Whenever possible, to ensure that subjects take the capsule on the day of cue reactivity, subjects should either self-report taking their study medication earlier that day or take their study medication while observed by study staff just

before the cue reactivity session. If the subject, for whatever reason, cannot take their study medication that day, they can be rescheduled to complete the cue reactivity paradigm.

After confirmation of eligibility for the H-LAB paradigm, subjects who use nicotine will have the opportunity to use it approximately 1 hour prior to starting the H-LAB paradigm. All subjects will be asked (but not required) to drink 4 oz of water and a restroom break prior to the lab session will be provided. Upon completion of clinical assessments, subjects will be escorted to a comfortable chair in a lighting-controlled, sound-attenuated room for alcohol exposure.

Subjects will be presented with either their *most commonly consumed* alcoholic beverage (e.g. vodka, lager beer) or bottled water. The alcohol or water beverage is presented in the subject's preferred mode of consumption (e.g., small tumbler for vodka, Pilsner glass for beer). Specific alcohol brand preferences are accommodated whenever possible, including choices of mixers (e.g., vodka will be poured into a glass along with orange juice if the favorite drink were a screwdriver).

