The H-LAB paradigm will follow our standardized procedures. Audio-recorded instructions ensure standardization within and across subjects. After attaching the physiological monitor (i.e., blood pressure cuff), the session begins with a 3-minute relaxation period that involves subjects sitting quietly and doing nothing. Then a 3-minute water trial begins, in which subjects hold and smell a glass of water as a standard procedure to control for the effects of simple exposure to any potable liquid, including all aspects of stimuli and movement except the nature of the beverage. A second 3-minute relaxation period follows the water trial. Next, subjects hold and smell a glass of their most desired or commonly consumed alcoholic beverage for two consecutive 3-minute alcohol trials. Order of water and alcohol trials is not counterbalanced due to known carryover effects. The water is accompanied by a commercially labeled water bottle and alcohol by the bottle or can from which it was poured and prepared as the teen usually drinks it. Across water and alcohol trials, subjects sniff the beverage for 5 seconds each time a tone sounds: 13 tones sound at variable intervals during each 3-minute block to ensure that all youth receive the same olfactory exposure. Observation via one way window ensures compliance. Subjects rate their alcohol craving after each 3-minute trial.

After every 3 minutes of exposure, each subject will rate his/her urge to drink alcohol using a visual analogue scale (VAS). The primary efficacy endpoint in the H-LAB is the "strength" of alcohol craving measured on a visual analogue scale (VAS; Item 1 below).

Following the H-LAB paradigm, subjects will receive a 7-day supply of the blinded study medication, and the dosing schedule will be reviewed. The subject will be instructed to bring the blister cards with them to the next visit so the project staff can perform drug accountability (capsule counts). The subject will also be instructed to contact project staff if they are experiencing any intolerable adverse events.

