5.3 Investigational Product Discontinuation

Subjects who are discontinued from investigational product should continue in the study and complete all assessments, including the follow-up assessments, as well as *Path 180*. If the subject discontinues the investigational product before Study Week 5 then they will not complete the H-LAB paradigm.

- a. **Pregnancy.** Females who become pregnant during the medication phase of the study, Study Weeks 1 through 6, will be immediately discontinued from the investigational product. The investigator must report a pregnancy within 1 working day of the site being aware to the medical monitor.
- b. **Physical Illness.** Subjects will need to be removed from investigational products if they have a serious illness or a disabling condition that precludes them from taking the investigational product.

c. **Adverse Events.** If the subject experiences any AEs that are considered study drug related and for which the investigator has determined that continuation of the study drug could be detrimental to the health of the subject, then drug will be reduced for 1 week, then discontinued, or immediately discontinued as described above.

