8.1 Feasibility and Acceptability Endpoints

8.1.1 Primary Feasibility Endpoint

The number and percentage of subjects who completed the 6-week active medication phase will determine feasibility (target $\geq 70\%$).

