8.2 Secondary Outcome: Alcohol Craving Assessed in the H-LAB Paradigm

The secondary endpoint will be alcohol craving assessed during a laboratory alcohol-cue exposure paradigm, at study week 5. During the paradigm, participants rated their alcohol craving immediately following exposure to water cues and again immediately following exposure to alcohol cues. The primary outcome measure will be is the number and percentage of participants who report any level of alcohol craving during a laboratory alcohol-cue exposure paradigm (following exposure to alcohol cues) using the following single item: *How strong is your craving to drink alcohol?* Scores range from 0 (None) to 20 (Extremely Strong). Individuals who endorse any level of alcohol craving (e.g., > 1) are considered to

experience craving. Individuals who do not report any alcohol craving (e.g., 0) will be regarded as non-craving. Using generalized estimating equations, we compared the likelihood of alcohol craving as a function of medication condition.

Quality Control and Quality Assurance

This study will be conducted under International Conference on Harmonization (ICH) Good Clinical Practice (GCP) guidelines and all applicable regulatory requirements.

Actions to ensure the accuracy and reliability of data include the selection of qualified investigators and appropriate study centers; the review of protocol procedures with the investigator and study personnel prior to study start; the design of suitable source documents with appropriate instructions for use; the internal audit of source data according to GCP and internal procedures to ensure their accuracy, completeness, and verifiability; as well as the periodic site monitoring by the Sponsor's representatives (clinical monitors). The Project Coordinator or Project Director will review source documents and CRFs for accuracy and completeness. Any discrepancies will be resolved with the investigator, as appropriate.

Audits and Inspections

Authorized representatives of the Sponsor and the IRB may visit the site to perform audits or inspections, including source data verification. The purpose of the audit or inspection is to systematically and independently examine all study related activities and documents to determine whether these activities were conducted, and data were recorded, analyzed, and accurately reported according to the protocol, GCP guidelines, and any applicable regulatory requirements.

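### The week-5 craving comparison in section 8.2 ignores the pre-dose alcohol-cue rating that the trial already collects, and so may give up precision at 21 subjects per arm

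*Combined protocol and SAP*

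**What the plan says.** Section 8.2 defines the outcome as the number and percentage of subjects reporting any craving after alcohol cues at week 5, on a single 0-20 item. The whole analysis specification is: "Using generalized estimating equations, we compared the likelihood of alcohol craving as a function of medication condition". Medication condition is the only term named. Section 6.2 adds none.

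The cue session is held twice. Section 4.7: "During the Randomization/Baseline Visit (prior to taking the study medication) and in Study Week 5, subjects will be seen in-person in the clinic". Section 4.6.5 says that at week 5 "subjects will complete a second H-LAB paradigm session, which will follow the same procedures as the pretreatment baseline assessment session". Within a session, "Subjects rate their alcohol craving after each 3-minute trial"; there is one water trial and there are two alcohol trials. An inclusion criterion in section 4.3.1 reads "Complete all assessments required at screening and baseline". A pre-dose alcohol-cue rating should therefore exist for every randomised subject, although this is inferred from these sections and not stated outright.

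Section 4.6.1 balances on sex alone: "Urn randomization will ensure approximately equal representation of males and females". Sex is not named in the analysis either.

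**The concern.** The pre-dose rating is the same item, from the same procedure, in the same subject. It is the most obvious candidate predictor of week-5 craving, and the plan never says how it will be used. Section 1.2 itself notes that cue reactivity differs from person to person. Adjusting for baseline removes whatever part of that variation is stable between the sessions.

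The trial has little precision to spare. The target is 21 per group, and section 5.3 reduces the week-5 data further: "If the subject discontinues the investigational product before Study Week 5 then they will not complete the H-LAB paradigm". The comparison also carries weight, because the synopsis and section 2.1 list the craving hypothesis among the primary objectives even though sections 6.2 and 8.2 label the outcome secondary. Leaving the covariates unnamed also leaves the model open to choice at the analysis stage.

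**Working it through.** **Inputs from the documents.** 50 randomised at about 1:1, with 21 per group (42) targeted to complete (section 1.4); a binary week-5 endpoint and a 0-20 rating (section 8.2); a completion target of at least 70% (section 8.1.1). The plan gives no power, alpha, craving rates or correlation for this comparison, so there is no stated figure to reproduce.

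**Assumptions.** Two-sided 5% level. One yes/no week-5 value per subject. Craving 70% on placebo and 40% on atomoxetine, with 90% and 60% as an alternative. Underlying craving at the two sessions is bivariate normal with latent correlation 0 to 0.7. The baseline rating is 6 + 6z, rounded and clipped to 0-20. Sex is balanced within arm and has no effect.

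**Unadjusted precision.** Half-width of the 95% interval for the risk difference = 1.96 × √[(0.70×0.30 + 0.40×0.60)/21] = 1.96 × √(0.45/21) = 1.96 × 0.1464 = 0.287.

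**Adjusted precision and power.** The adjusted estimate comes from a logistic model with treatment and baseline rating, with predicted risks averaged over the sample (a standardised risk difference). There were 12,000 simulated trials per correlation. Power is for likelihood-ratio tests, with critical values set to equal size from 20,000 null trials at 55% craving. Adjusted half-width = 0.287 × √(variance ratio).

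| Latent correlation | Variance ratio | 95% half-width | Power %, unadjusted to adjusted |
|---|---|---|---|
| 0 | 1.021 | 0.29 | 49.6 to 49.4 |
| 0.3 | 0.975 | 0.28 | 49.9 to 51.9 |
| 0.5 | 0.861 | 0.27 | 50.6 to 55.6 |
| 0.7 | 0.720 | 0.24 | 49.9 to 64.2 |

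In sample-size terms, ratios of 0.861 and 0.720 correspond to 21/0.861 = 24.4 and 21/0.720 = 29.2 subjects per arm. An independent simulation under the same assumptions gave ratios of 1.02, 0.97, 0.87 and 0.72, with the standardised difference unbiased near -0.30.

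**Cross-check.** To a first approximation the variance ratio is 1 - r², where r is the observed correlation between the baseline rating and week-5 yes/no craving within an arm. Latent 0.5 and 0.7 correspond to observed values of about 0.36 and 0.50 in the control arm: 1 - 0.36² = 0.87 and 1 - 0.50² = 0.75, close to the table. If the observed correlation were itself 0.5 or 0.7, the ratios would be about 0.75 and 0.51.

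**Other scenarios.**
- 90% vs 60%: unadjusted half-width 1.96 × √[(0.09 + 0.24)/21] = 0.246. Variance ratios 1.020, 0.987, 0.900 and 0.783 at latent 0, 0.3, 0.5 and 0.7.
- Only the completion target met: 0.70 × 50 = 35, about 17 per arm. Unadjusted half-width 1.96 × √(0.45/17) = 0.319. Variance ratios 1.035, 0.968, 0.852 and 0.737. Power went from 42% to 45% (latent 0.5) and from 40% to 54% (latent 0.7). The two unadjusted figures differ only through simulation noise (3,000 trials).
- Adding sex: ratios 1.022, 0.977, 0.864 and 0.722, a change of under 1% from baseline alone, with no gain in power.

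**Test behaviour.** The adjusted likelihood-ratio test ran at 5-6% type I error (6-7% with sex). A residual permutation test gave 4.7, 4.3, 4.8 and 3.4% across the four correlations, with power of 50, 51, 54 and 65%. Separation occurred in under 1% of trials at 70% vs 40% and in about 12% at 90% vs 60%.

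**The case against.** The best defence is that nothing here is an error. The unadjusted comparison is valid, this is a proof-of-concept trial, and sections 6.2 and 8.2 call the outcome secondary. The benefit rests on a correlation that the documents do not supply. At latent 0.3 it is worth about two points of power, at zero it costs about 2% in variance, and even at 0.7 power is only 64%. All of that stands, and it limits the point to one of efficiency.

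It can also be said that the model being amended is undefined. Generalised estimating equations suggest repeated records, but section 8.2 does not say which, and baseline might have been meant to enter as a repeated outcome. Section 4.7 further names craving strength, not any-versus-none, as the primary efficacy measure in the laboratory session. These matters need settling, but a baseline covariate works whichever week-5 records are clustered. If baseline was meant to be a repeated outcome, the text has to say so.

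Third, the change may come late. Section 8.2 is written in the past tense, the estimated last completion in the synopsis was 03/31/2022, and a page is dated 28APR2025. The documents do not show whether unblinded results have been seen. If they have, the change of main analysis is no longer available and a labelled sensitivity analysis is the proper course.

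Two smaller objections also stand. The 17-per-arm case treats six-week completion as a stand-in for week-5 attendance. Simulating no sex effect guarantees that sex shows no gain.

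**Conclusion.** The concern holds. Section 8.2 names no covariate, while the same alcohol-cue rating is taken before the first dose. Under the main assumptions (70% vs 40%, 21 per arm), adjusting for it cuts the variance of the risk difference by 14% to 28% at latent correlations of 0.5 to 0.7, narrows the half-width from 0.29 to 0.27 or 0.24, and raises power from about 50% to 56% or 64%. At latent 0.3 or below there is practically no gain, and an uninformative baseline costs 2-3% in variance. The craving rates, alpha and correlations are assumptions, so the size of the benefit is uncertain. Adjustment repairs neither the small sample nor the missing week-5 data.

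**What to change.** In section 8.2, specify:

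- **Covariates:** the pre-dose alcohol-cue rating, taken as the mean of the two alcohol trials and kept continuous on 0-20 (a yes/no baseline says little if nearly everyone craves at entry), plus sex as the balancing factor, with only a small gain expected.
- **Effect measure:** a standardised (marginal) risk difference with 95% CI. This keeps the comparison of percentages that section 8.2 describes; a covariate-adjusted odds ratio would be conditional and answer a different question.
- **Test:** a permutation p-value fixed in advance, because the adjusted likelihood-ratio test runs slightly above 5%.
- **Separation:** a written rule that a penalised fit is used only if separation occurs. Routine penalisation shrinks a true difference of -0.30 to about -0.28.
- **Exclusion:** no adjustment for week-5 water-cue ratings, which are post-randomisation.
- **Structure:** which records the estimating equations treat as repeated.

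If unblinded results have already been seen, keep the existing comparison as the main one and report the adjusted model as a labelled sensitivity analysis.

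The cost is a few sentences and modest extra analysis. Both variables are already collected, so no new data or subjects are needed.

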1.4 General Investigative Plan

This proof-of-concept study is a double-blind, randomized, placebo-controlled, parallel group, single-site clinical trial. After obtaining consent/parent permission/assent, potential subjects and, if younger than 18 years, their parent(s) will complete a medical history and psychiatric diagnosis interview (about the adolescent) to screen for eligibility. Youth will also complete a physical examination, vital signs, drinking history by the timeline follow-back (TLFB) method, alcohol breathalyzer test, Clinical Institute Withdrawal Assessment for Alcohol-revised (CIWA-AR), prior/current medication use, urine toxicology screen, clinical chemistry, and the Columbia Suicide Severity Rating Scale (CSSR-S). Females of child-bearing potential will have a pregnancy test.

If eligible for the study, 50 subjects will be randomized in an approximate 1:1 ratio (targeting 21 subjects per group – 42 subjects total who complete the protocol) to either atomoxetine or placebo for 6 weeks.

Atomoxetine will be dosed at 40 mg/day for three days then increased to the maintenance dose of 80 mg (active) taken orally once daily (QD) for an additional 5.5 weeks. Subjects randomized to the placebo condition will be given an equal number of visually matched capsules.

As shown in Figure 1, subjects will be seen in the clinic (or remotely) at the screening appointment, the randomization/baseline session, and at weekly visits during the study. At the randomization/baseline visit and after 4 weeks of investigational product administration (i.e., Study Week 5), subjects will undergo a human laboratory paradigm (i.e., alcohol cue reactivity assessment).

[figure not shown]

Figure 1: Overview of Study Chronology

Study Objectives

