6.2 Secondary Outcome: Alcohol Craving Assessed in the H-LAB Paradigm

The secondary endpoint will be alcohol craving assessed during a laboratory alcohol-cue exposure paradigm, at week 5. During the paradigm, participants rated their alcohol craving immediately following exposure to water cues and again immediately following exposure to alcohol cues.

The primary measure of alcohol craving will be the number and percentage of participants who report any level of alcohol craving during a laboratory alcohol-cue exposure paradigm using the following single item: *How strong is your craving to drink alcohol?* Scores range from 0 (None) to 20 (Extremely Strong). Individuals who endorse any level of alcohol craving (e.g., > 1) are considered to experience craving. Individuals who do not report any alcohol craving (e.g., 0) will be regarded as non-craving.

Safety Monitoring Plan

Safety monitoring will be conducted throughout the study; therefore, safety concerns will be identified by continuous review of the data by the principal investigator, clinic staff, medical monitor, and study nurses and physicians.

The Brown University IRB, medical monitor, principal and sub-investigators, and study nurses and physicians will review any safety concerns throughout the trial. In addition, a DSMB will participate in this study.

Quality control is central to all aspects of the activities detailed in this proposal to ensure clinical data accuracy and integrity. Day-to-day oversight of data quality will be delegated to the principal investigator, [name] and/or his designee. With assistance from our core team, he will provide direction with the development of data collection forms, recruitment and tracking databases, data management tasks, and statistical analyses and interpretation. The principal investigator or his designee will oversee the production of standard labels/codebooks for all data collection activities. He or his designee will oversee the production of reports that will track indices of project success, which will be reviewed weekly or biweekly at meetings of our core team, where issues or concerns will be deliberated and corrective action plans put into place.

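### Section 8.2 names GEE for a yes/no craving outcome in about 17–21 participants per arm but sets no rule for an arm at 0% or 100%; in its usual form the test can then give an extreme p-value from a one-participant difference

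*Combined protocol and SAP*

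**What the plan says.** Section 6.2 defines the craving measure as "the number and percentage of participants who report any level of alcohol craving during a laboratory alcohol-cue exposure paradigm", based on one item scored 0 to 20. Section 8.2 repeats this, specifies the rating after alcohol cues at week 5, and adds the whole of the analysis: "Using generalized estimating equations, we compared the likelihood of alcohol craving as a function of medication condition".

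Neither section states the link function, the working correlation, a robust or model-based standard error, a Wald or score test, which ratings enter as rows, the significance level, or what happens when an arm has no non-cravers. Section 4.7 describes a water trial and two consecutive alcohol trials per session, with sessions at baseline and week 5, so several row structures are possible.

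On numbers, section 1.4 randomizes 50 at about 1:1, "targeting 21 subjects per group – 42 subjects total who complete the protocol". Section 8.1.1 sets a completion target of at least 70%. Under section 5.3, anyone who stops the product before week 5 has no second laboratory session. No craving rate, effect size or power is given anywhere.

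**The concern.** When every participant in one arm craves, the log-odds for that arm has no finite estimate. A likelihood-based logistic model signals this with an enormous standard error. A GEE with the robust (sandwich) standard error does not. Residuals in the all-craving arm are close to zero, so that arm adds almost nothing to the estimated variance, while the coefficient drifts to about −20. The Wald ratio becomes huge and the software prints a very small p-value.

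The outcome could sit near a ceiling. Participants have alcohol use disorder, hold and sniff their usual drink, and count as craving on almost any non-zero rating. Section 8.1 contains only descriptive targets, so this is the one test comparing the arms. A difference of a single participant, in either direction, could be reported as a drug effect.

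**Working it through.** **The plan's own figure.** 2 × 21 = 42, and 42/50 = 84%, so the sample size allows for 16% loss. The documents give no inputs for power, so nothing further can be reproduced.

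**Inputs.**
- 21 per arm: completer target, section 1.4.
- 17 per arm: 0.70 × 25 = 17.5, from the completion target in 8.1.1. This is an inference, not a stated number.
- Shared craving rate p: not stated. 70–95% is assumed.
- Two-sided 0.05: assumed.
- Logit link, robust standard error, Wald test, one row per person: assumed as the usual form.

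**Step 1: one table by hand.** Take 20/21 against 21/21. The mixed arm contributes variance 1/20 + 1/1 = 1.05, and √1.05 = 1.02. The fitted GEE (statsmodels) gives coefficient −21.6 and robust SE 1.02, so z is about −21 and p = 2e-98. For the same table, Fisher gives p = 1.00 and the score test p = 0.31. Similarly, 19/21 against 21/21 gives p = 6e-198 (Fisher 0.49), and 16/17 against 17/17 gives p = 2e-90 (Fisher 1.00). A bias-corrected sandwich does not help (p = 2e-89 for 20/21 against 21/21).

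**Step 2: when it does not happen.** For 20/21 against 21/21, the model-based SE is about 47,000 (p = 0.9996), and an identity or log link gives p = 0.31–0.32. With both arms at 100%, the difference is 0 and p = 1.00.

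**Step 3: row structure.** With an extra water or baseline row at 12/21 in each arm, the medication main effect gives p = 0.77–0.90, with no false signal. A medication-by-row interaction brings the failure back (p = 7e-94 under independence; SE not computable under exchangeable). If the placebo arm is at 21/21 on both rows, the main effect fails again (p = 2e-107).

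**Step 4: how often under no effect.** With q = pⁿ, the chance that exactly one arm is at 100% is 2q(1 − q). At p = 0.90 and n = 21, q = 0.90²¹ = 0.109, so 2 × 0.109 × 0.891 = 19.5%. Type I error comes from summing the binomial probabilities of all tables that reject. For the Wald test, tables with exactly one arm at 0% or 100% count as rejections, as the fits showed.

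| Shared craving rate | Exactly one arm at 100% (n = 21 / 17) | Robust Wald GEE type I error (n = 21 / 17) | Score test type I error (n = 21) |
|---|---|---|---|
| 70% | 0.1% / 0.5% | 4.5% / 4.1% | 5.6% |
| 80% | 1.8% / 4.4% | 4.5% / 5.7% | 5.2% |
| 85% | 6.4% / 11.8% | 7.5% / 12.2% | 5.1% |
| 90% | 19.5% / 27.8% | 19.7% / 27.8% | 4.1% |
| 95% | 44.9% / 48.7% | 44.9% / 48.7% | 1.3% |

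A 10% chance of exactly one arm at 100% needs a rate of at least 0.87 with 21 per arm, or 0.84 with 17. The chance cannot exceed 50%.

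**Step 5: power.** At 90% against 60% with 21 per arm, the same enumeration gives 65% for the score test, 61% for the robust Wald GEE and 52% for Fisher.

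**The case against.** A reader might infer that the plan specifies a logistic GEE which fails whenever an arm is at 100%, that this is likely here, and that any resulting effect is false. The documents do not support that reading.

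- **The method is not stated in that detail.** Section 8.2 names GEE only. The failure needs logit link, robust standard error and Wald test together, plus a row structure in which the separated cell drives the medication term. Several ordinary choices avoid it.
- **No craving rate is given.** Section 1.2 says some people show little or no rise in craving to cues. Participants want to cut down and are retested after four weeks of product and counselling. The cut-point also matters. Section 8.2 says "Individuals who endorse any level of alcohol craving (e.g., > 1) are considered to" experience craving and gives 0 as non-craving, so a score of 1 fits neither example; coding it as non-craving lowers the rate. Against this, the endpoint is the absolute rating after alcohol cues, not the rise over water, so non-reactors with a steady low urge still count. These points do not settle the rate in either direction.
- **Not every such table is a null result.** 16/21 against 21/21 has Fisher p = 0.048. This changes the totals little: counting only tables with one arm at 100% and Fisher p above 0.05, the rate at 90% craving is still 18.3% (n = 21) or 27.1% (n = 17).
- **The counts would be visible.** Numbers and percentages are part of the outcome, so an attentive reader would notice 21/21 against 20/21. That is a safeguard, but not a pre-specified rule.

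The first two points stand and limit the claim. They do not remove it, because the safe versions help only if the plan chooses one.

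**Conclusion.** The concern holds conditionally. Section 8.2 leaves open every choice that decides whether its test is valid when one arm is at 0% or 100%, and the usual form of the named method is not valid there. With logit link, robust Wald test and one week-5 row per person, type I error is acceptable at shared craving rates up to about 80%, and at 90–95% is about 20–49% across 17 to 21 per arm. These rates are assumptions; the documents neither give one nor show that a ceiling is likely. The fits come from one software package, and the exact size of the extreme p-values depends on where iteration stops.

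This is a cheap and worthwhile improvement, not a fault that invalidates the plan. The outcome is labelled secondary in 6.2 and 8.2, although the synopsis and section 2.1 list the craving question as a primary objective.

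**What to change.** In section 8.2:

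1. Make the main test a comparison of week-5 craving proportions by score test (or Fisher's exact test), with a Miettinen-Nurminen interval for the risk difference. If covariates are kept, use Firth-penalised logistic regression with profile-likelihood inference.
2. State how the two alcohol-trial ratings become one yes/no, and how a score of 1 is coded.
3. Keep the GEE as a sensitivity analysis with link, standard error, test and rows stated. Do not report its Wald p-value when an arm is at 0% or 100%.
4. Section 8.2 is in the past tense, so the analysis may already have been run. If so, report craving counts by arm, and do not rely on a GEE Wald p-value if one arm is at 0% or 100%.

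The cost is a few lines of text and code. In the case checked, the score test loses no power against the GEE (65% v 61%). It becomes conservative at very high craving rates (type I error 1.3% at 95%, 21 per arm). Fisher is more conservative throughout and gives up power in the same case (52%), which favours the score test unless strict error control is wanted.
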